#### Investigator Responsibilities

A. The Investigator submits any serious adverse event that requires reporting according to this policy and any other adverse event that may represent an unanticipated problem involving risk to participants or others as follows:

1. A "Report of Unanticipated Problem Involving Risk to Participants or Others" is submitted to the IRB as soon as possible, but no later than 7 calendar days after the Investigator first learns of the event or problem.

This form contains the Investigator's assessment of causality (related or not related to the study) and a description of the actual event;

2. The form also contains an evaluation of whether the event meets the following criteria:

- a. An event that suggests that the research places subjects or others at a greater risk of physical or psychological harm than was previously known or recognized;
- b. Unanticipated (i.e., the event was not foreseeable); and
- c. Related (i.e., likely to have been caused by the research procedures)

3. Finally, any associated materials such as medical record notations or reports with the name and medical record number of the individual redacted (removed) will be included with the report.

4. When applicable, a “Request for Amendment” indicating changes associated with the event or problem is submitted.

#### *Serious Adverse Event (SAE) Reporting*

The Division of AIDS Table for Grading the Severity of Adult and Pediatric Adverse Events (DAIDS AE Grading Table), Version 1.0, December, 2004, will be used to determine clinical and laboratory grades of any/all grade 2 or higher events (including signs and symptoms, laboratory abnormalities, and diagnoses).

In addition, any/all deaths, disabilities, malignancies, and/or any other conditions deemed serious and/or debilitating/incapacitating by the clinical team will be reported to all involved ethical review boards. The PI will submit SAE information as required by local regulatory or other local authorities, and the research team will adhere to these stringent requirements and submit full reports detailing any SAEs in a timely fashion (i.e. in accordance with existing standards). After the end of the protocol-defined SAE reporting period stated above, the site will report serious, unexpected, clinical suspected adverse drug reactions if the study site staff becomes aware of the event on a passive basis, i.e., from publicly

#### Benefits

Traditional healers in this study could potentially benefit from training on HIV testing protocols as this opens up a new avenue for paid employment in the future. For community members, it provide a new, less stigmatized avenue to access HIV counseling and testing.

#### **9. Limitations**

This pilot study is not a randomized controlled trial, thus we cannot compare uptake of healer-initiated testing with other modalities; however, we will capture uptake of healer-initiated testing, impact of uptake on key psychological outcomes, including HIV stigma and mistrust in the health system, and obtain data on linkage of participants to the health system - key elements to developing and powering a larger randomized controlled trial. We have framed the intervention and subsequent analysis in the cultural context and are collecting data to specifically identify/inform subgroup effects, including sex. While we may be underpowered to detect some of these effects in small subgroups, a low p-value on heterogeneity tests will provide us with a signal for further investigation in a sufficiently powered future RCT.

#### **10. Dissemination Plan**

Results of this study will be collected into a report and shared with the national, provincial and local Departments of Health, traditional healers and biomedical practitioners in the Bushbuckridge area, and researchers at the University of Witwatersrand and Vanderbilt University and the Agincourt research community. Results of this study will also be presented in peer-reviewed journals and at conferences.

## Appendices

### Appendix 1: Surveys for health care providers

As a health care worker...

I would prefer to not provide services to immigrants here illegally

I believe that illegal immigrants put clinicians at higher risk of acquiring HIV

I agree that illegal immigrants engage in immoral behavior

I agree that illegal immigrants deserve their HIV diagnosis.

I would prefer to not provide services to patients who prefer traditional medicine

I believe that people who use traditional medicine put clinicians at higher risk of acquiring HIV

I agree that people who use traditional medicine engage in immoral behavior

I agree that people who use traditional medicine deserve their HIV diagnosis.

I would prefer to not provide services to young unmarried, pregnant girls

I believe that young, unmarried pregnant girls put clinicians at higher risk of acquiring HIV

I agree that young, unmarried pregnant girls engage in immoral behavior

I agree that young, unmarried pregnant girls deserve their HIV diagnosis.

I would prefer to not provide services to men who have sex without a condom.

I believe that men who have sex without condoms put clinicians at higher risk of acquiring HIV

I agree that men who have sex without condoms engage in immoral behavior

I agree that men who have sex without condoms deserve their HIV diagnosis.

I would prefer to not provide services to sex workers.

I believe that sex workers put clinicians at higher risk of acquiring HIV

I agree that sex workers engage in immoral behavior

I agree that sex workers deserve their HIV diagnosis.

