## *Clinician outcomes:*

We will assess baseline, midterm (after the first training) and end line (after the second training) stigma levels among providers using a Likert-style scale that will assess attitudes towards PLHIV, traditional healers (and healers providing HIV testing in the community), people who use traditional healers, sex workers, men who have sex with men, immigrants, young pregnant women who are not married, and sex workers. We will ask if health care workers: (1) would prefer to not provide services; (2) believe that sub-populations put clinicians at higher risk of acquiring HIV; (3) agree that specific populations engage in immoral behavior; and (4) agree that specific populations deserve their HIV diagnosis.

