Health care providers will receive training in stigma reduction and structural changes to engage these previously stigmatized populations. We will focus on four essential elements identified by Nybalde (1) Participatory learning via the provision of information about the impact of stigma on health care outcomes and; (2) Skill building activities (communication, openness) with health care providers to develop skills to work with stigmatized populations (3) Contact with the stigmatized group, including healers and their patients via testimonials and (4) group activities to develop empathy, humanize this stigmatized group, and break down stereotypes.

The stigma reduction training will be conducted by clinician-trainers based at the University of the Witwatersrand. The first part of the training will include an initial two-day training followed by a one-day training two months later that include the following components:

Title of exercise/session	Educational technique	Intended learning outcomes
1. Naming stigma through pictures	In this session, prepared pictures based on personal stories of stigma are viewed. Then, the participants discuss and analyze the forms, causes, and effects of stigma.	Participants discuss what similar stigma takes place in different contexts and start to share stories of what they have personally witnessed.
2. Our own experiences of stigma	This exercise asks participants to think about a time in their life when they felt stigmatized, share this with a partner, and discuss with the larger group	Gives participants a better understanding of the personal feeling and the long-term impacts of stigmatization
3. Key populations stigma problem tree	Using colored cards and markers, participants discuss and write forms of stigma faced by key populations at risk of HIV. The cards are posted on a wall with the causes of stigma representing "roots"	Helps participants to recognize the causes of stigma and how the resulting effects are manifested.

	of a tree at the bottom, actual forms of stigma as the “trunk” of the tree in the middle, and effects of stigma as the tree’s leaves and branches.	
4. Value clarification	Participants fill and individual questionnaire about their personal values and reflect and discuss how these values affect their judgement of others.	Recognition of how personal attitudes and beliefs influence stigmatizing behavior.

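### The clinician stigma outcome and the provider survey disagree: three of the seven groups named in the outcome have no items in Appendix 1

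*Combined protocol and SAP*

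**What the plan says.** Section 5 (Clinician outcomes) describes a Likert-style scale given to providers at baseline, after the first training and after the second. It is to cover "attitudes towards PLHIV, traditional healers (and healers providing HIV testing in the community), people who use traditional healers", followed by "sex workers, men who have sex with men, immigrants, young pregnant women who are not married, and sex workers". Sex workers appear twice in that list.

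Four questions follow, starting with "We will ask if health care workers: (1) would prefer to not provide services". The other three ask whether the group raises the clinician's own risk of HIV, whether it behaves immorally, and whether it deserves its diagnosis.

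Appendix 1, the survey for health care providers, puts these four questions to five groups. The blocks open with:

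- "I would prefer to not provide services to immigrants here illegally"
- "I would prefer to not provide services to patients who prefer traditional medicine"
- the same stem for young, unmarried pregnant girls
- "I would prefer to not provide services to men who have sex without a condom"
- the same stem for sex workers

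Section 5 (Training Activities) lists among the elements of the provider training "Contact with the stigmatized group, including healers and their patients via testimonials". Session 6 of the training table is devoted to traditional healers and HIV.

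**The concern.** The four stems in Appendix 1 match the four questions in Clinician outcomes one for one, so the appendix is evidently the instrument meant for this outcome. The groups, however, do not match. A provider who completes the printed form is never asked about people living with HIV, traditional healers or men who have sex with men.

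What is at stake is whether the pilot can describe change in attitudes that its own training sets out to alter. The training brings providers into contact with healers as well as with their patients, but the printed form asks only about the patients. A baseline that was not collected cannot be recovered later. Section 9 presents the pilot as groundwork for a larger randomized trial, so a gap in the instrument could carry forward into that trial.

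**Working it through.** The plan gives no figure to reproduce. The check is a group-by-group match. The outcome list is taken from Clinician outcomes, with sex workers counted once and healers who test for HIV counted with healers. The survey blocks are taken from Appendix 1.

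| Group in the stated outcome | Block in Appendix 1 |
|---|---|
| People living with HIV | None |
| Traditional healers, including those who test | None |
| People who use traditional healers | Yes: people who prefer or use traditional medicine |
| Sex workers | Yes |
| Men who have sex with men | None |
| Immigrants | Partly: only those present illegally |
| Young unmarried pregnant women | Yes |
| Not named | Men who have sex without a condom |

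**Groups.** The outcome names 3 + 4 = 7 distinct groups. Four have a block, one of them in narrower form. 7 − 4 = 3 have none.

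**Items.** Appendix 1 prints 5 blocks × 4 questions = 20 items. Of these, 4 × 4 = 16 concern a group in the outcome. The other 20 − 16 = 4 (4/20 = 20%) concern a group that the outcome does not name.

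**Size of the gap.** Asking all four questions about the three missing groups takes 3 × 4 = 12 items. If healers who test for HIV are counted as a separate group, the gap is 4 of 8 groups and 4 × 4 = 16 items.

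**Near matches.**

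- Each block ends with an item on deserving an HIV diagnosis. These five items touch on blame for HIV, but only within another named group, so they give no separate measure of attitudes to people living with HIV.
- People who use traditional medicine are patients. The outcome lists them separately from healers.
- Sex without a condom is a different attribute from sex between men, whatever the intention behind the wording.

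**Waves.** Clinician outcomes plans three provider surveys. Measurement of Results and Data Collection describe two, at study start and just after the study ends. The missing groups are unobserved on either schedule.

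**The case against.** The strongest reply is that Appendix 1 may not be the complete form. It shows no response options or scoring, although a Likert-style scale is promised. Appendix 2 is visibly incomplete too: it omits the demographics, belief in the HIV test and use of traditional medicine that Table 6 says will be collected. A reader might infer from the appendix that the three groups cannot be measured. The documents do not support that, because absence from an appendix does not prove that nothing will be asked. Against this reply, Appendix 1 is not labelled an extract and the documents contain no other provider instrument. The disagreement between the two sections therefore stands, and the consequence is conditional on the printed form being used.

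A reader might also infer that the study's focal group has been left out. That goes too far. Training Activities and Section 6.2 name healers together with their patients. The patients are the people recruited, and they have a full four-item block. People living with HIV are not central to the main analysis either: community members with an earlier positive result are excluded, and Section 4 expects only 10 to 30 positive tests.

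Nor can 12/28 = 43% of items be called missing. The 28 assumes that every question applies to every group, whereas the text speaks only of sub-populations and specific populations. The count of three groups in seven needs no such assumption.

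Finally, the measure is ancillary. It is absent from the hypothesis in Section 2, the sample size in Section 4, the endpoints in Table 3 and the analysis in Section 7. That limits how much the gap matters but does not remove the contradiction.

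**Conclusion.** The two sections disagree and need to be reconciled. Three of the seven groups in the stated clinician outcome have no items, one block concerns a group outside the outcome, and one group is narrowed. The count rests on treating sex workers as one group and healers who test as part of healers. The loss of information rests on the survey being fielded as printed.

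On that condition, the study would learn about provider attitudes to people who use traditional medicine, but nothing about attitudes to healers, to people living with HIV in general, or to men who have sex with men. No primary result is affected. The correction is worth making because it is cheap before the baseline wave and cannot be made good afterwards. The documents do not show whether the condom-use wording is a slip or deliberate, so it needs an explanation and cannot simply be presumed wrong.

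**What to change.** Before the baseline provider survey:

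1. Add the Clinician outcomes questions for people living with HIV, for traditional healers (including those who provide HIV testing) and for men who have sex with men. This is up to 12 items. Some stems, such as deserving an HIV diagnosis, fit healers poorly and should be adapted.
2. Correct the block on men who have sex without a condom, or state why it is there and add that group to the outcome.
3. Align the immigrant wording in the two sections, or justify the narrower form.
4. Define the clinician stigma score on the groups actually asked, and remove the duplicate mention of sex workers.

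If the sponsor prefers not to lengthen the survey, narrowing the outcome text to the groups in Appendix 1 would also remove the contradiction. It would mean giving up any measure of stigma towards healers and people living with HIV. If a fuller form already exists, appending it would settle the matter.

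The cost of the main option is about 12 short items per provider survey and an ethics notification of the revised form.

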### Appendix 2: Surveys for participants

#### A. Adapted items from the Group-Based Medical Mistrust Scale (GBMMS) Items

People like me cannot trust doctors and health care workers.

People like me should be suspicious of modern medicine.

People like me should be suspicious of information from doctors and health care workers.

People like me should not confide in doctors and health care workers because it will be used against them.

Doctors and health care workers treat people like me like guinea pigs.

People like me receive the same medical care from doctors and health care workers as people from other groups.

People like me are treated the same as people of other groups by doctors and health care workers.

In most hospitals, people of different backgrounds receive the same kind of care.

Doctors have the best interests of people like me in mind.

Doctors and health care workers sometimes hide information from people like me.

I have personally been treated poorly or unfairly by doctors or health care workers because of who I am.

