## **2. Objectives**

The objective of this proposal is to conduct a pilot test of a program aimed at training traditional healers to conduct HIV testing and implementing HIV testing among people living in Bushbuckridge, South Africa.

Pilot Healer-initiated HIV testing uptake and linkage to prevention services. Trust in allopathic health care and HIV stigma will be measured among participants at study enrollment and at month seven.

*Hypothesis:* HICT will increase trust in allopathic health care and reduce HIV stigma.

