#### Patient Outcomes

**Primary Continuum of Care Endpoints:** (1) Uptake of health facility HIV-test at 6-months (if previously negative or refused test), (2) Uptake of ART services, if positive.

**Secondary Endpoints:** (1) Mistrust towards the allopathic health system, (2) Change in levels of HIV-related stigma among those who test negative, (3) Change in levels of conspiracy beliefs

**Feasibility Outcome:** (1) Uptake of healer-based HIV testing

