## **8. Ethical Considerations**

### Recruitment and Consent

Participants will be recruited among those who present for health care services from one of our traditional healers trained in conducting HIV counseling and testing. Participants will be recruited after their healer consultation is completed to ensure we do not impact their services. Healers will screen potential participants for eligibility (no HIV test in past year, over 18 years of age, live in Agincourt) and if they are eligible, the healers will ask if they are willing to participate in a research study. Healers will state clearly that there is no obligation to participate and that choosing not to participate will in no way impact their health care from this traditional healer. Healers will consent participants via an online consent form via tablet, so all consent forms will be online and backed up to the secure Vanderbilt REDCap cloud.

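### Eight of the 11 mistrust items do not say whether traditional healers count as health care workers, so a change in how participants read them could pass for a change in trust in allopathic care

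*Combined protocol and SAP*

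**What the plan says.** Section 2 (Objectives) states the hypothesis that "HICT will increase trust in allopathic health care and reduce HIV stigma", with both measured at enrolment and at month seven. The outcomes table in section 5 (Patient Outcomes) lists "Mistrust towards the allopathic health system" as a secondary endpoint. The only printed scale that fits that endpoint is Appendix 2, section A, the adapted Group-Based Medical Mistrust Scale. The protocol does not name the link, but no other instrument matches.

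Of its 11 items, eight pair doctors with health care workers. The first is "People like me cannot trust doctors and health care workers" and the last is "I have personally been treated poorly or unfairly by doctors or health care workers because of who I am". The other three are "People like me should be suspicious of modern medicine", "In most hospitals, people of different backgrounds receive the same kind of care" and "Doctors have the best interests of people like me in mind". Section A prints no stem, definition or instruction about traditional healers. Section D of the same appendix and the provider survey in Appendix 1 do print stems.

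Under Recruitment and Consent (section 8, repeated under Study Procedures in section 5), participants are "those who present for health care services from one of our traditional healers trained in conducting HIV counseling and testing". The same paragraph has the healer assure patients that declining will not affect the health care they get from that healer.

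**The concern.** The endpoint concerns the allopathic system, but the term used in most of the items has an open edge. The person who delivers the intervention is a healer trained and certified to give an HIV test with pre- and post-test counselling. The Training Activities section says that community health workers already do home-based testing and counselling. Several items, on information, confiding and hiding things, fit that encounter.

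If the experience leads some participants to count the healer among health care workers at Month 7 when they did not at enrolment, the score can move without any change in how they see clinics. Participants chose to consult a healer, so the movement would probably be towards lower mistrust, as hypothesised. The Limitations section says that the study is not randomised, so no control group would expose the drift. Appendix 2 prints no separate measure of trust in healers. The Limitations section also says that these data are meant to help develop and power a larger randomised trial.

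**Working it through.** **Step 1: count the items (Appendix 2, section A).**

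- Items printed: 11.
- Items with the term health care workers: numbers 1, 3, 4, 5, 6, 7, 10 and 11, so 8. Share = 8/11 = 0.727.
- Of these, items that omit doctors: 0.
- Items that name or exclude healers: 0.

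**Step 2: what changes between the surveys.**

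- Healer status does not change. The inclusion and exclusion criteria require trained healers who passed certification, and participants are recruited from healers already trained.
- Participant experience does change. Table 6 lists the enrolment survey ahead of healer-initiated counselling and testing, both under Baseline, and repeats the trust measure at Month 7. Eligible participants have had no HIV test result in the past year.

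A person who includes healers at both surveys, or at neither, contributes little bias to a change score. Bias needs people who switch.

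**Step 3: how large the bias could be.** The plan gives no response options, scoring rule, SD, correlation or expected number of paired surveys for this scale, so it has no figure to reproduce. Everything below except the 8/11 is assumed:

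- 5-point items, equally weighted, scored so that higher means more mistrust
- SD of the mean item score 0.7 to 0.8, and correlation r between surveys 0.4 to 0.5
- 300 to 450 paired surveys (50% to 75% of the planned 600)
- a two-sided 5% paired test, normal approximation; the Data Analysis section specifies no test for this endpoint

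SE of the mean change = SD × √(2(1 − r)) / √n

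- Least precise: 0.8 × √1.2 / √300 = 0.051
- Most precise: 0.7 × √1.0 / √450 = 0.033

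Spurious shift = (share switching) × (points moved per item) × (items affected / 11)

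Probability of significance = Φ(shift/SE − 1.96) + Φ(−shift/SE − 1.96)

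| Switching | Points per item | Items affected | Shift | Probability of significance |
|---|---|---|---|---|
| 20% | 1 | 8 | 0.20 × 1 × 8/11 = 0.145 | 0.82-0.99 |
| 10% | 1 | 8 | 0.10 × 1 × 8/11 = 0.073 | 0.30-0.60 |
| 20% | 0.5 | 7 | 0.20 × 0.5 × 7/11 = 0.064 | 0.24-0.49 |
| 10% | 0.5 | 7 | 0.10 × 0.5 × 7/11 = 0.032 | 0.10-0.16 |
| 5% | 0.5 | 7 | 0.05 × 0.5 × 7/11 = 0.016 | 0.06-0.08 |

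The seven-item rows leave out item 11. It asks about past personal mistreatment, and adding a well-liked healer to the reference group does not undo that. With no true change the probability would be 0.05, so the last row is barely above the nominal rate.

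**The case against.** The strongest reply is that the wording already points to biomedical care. Every affected item pairs the term with doctors, and the other three refer to modern medicine, hospitals and doctors alone. The protocol also uses the term without a qualifier for facility staff, under Clinician outcomes and in Appendix 1, and section 6.2 lists health care workers separately from healers. This stands in part. A healer-only reading is unlikely, and at most trust in the healer blends into the answers. But respondents see the survey and not the protocol, and adding health care workers to doctors widens the group without saying how far.

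A reader might infer that the healer becomes a certified tester between the surveys. The documents do not support that, because certification precedes recruitment. Clients who already regard healers as health care workers may do so at baseline too, and a stable reading largely cancels.

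A reader might also infer that the pilot is likely to report a false gain in trust. The documents do not support that either. They give no switching rate, and the high probabilities come from the least favourable assumptions.

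Finally, the administered wording is not visible. The population mainly speaks xiTsonga, and a translation could already remove the ambiguity or could keep it.

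**Conclusion.** The point holds as a possible threat to construct validity, not a demonstrated bias. What the documents establish is that 8 of 11 items leave the reference group undefined, that the protocol itself calls healer services health care, and that participants' experience of the healer changes between the two surveys. That makes a shift in meaning plausible on a secondary endpoint tied to the stated hypothesis.

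The size cannot be settled from the documents. The range of 0.06 to 0.99 rests on assumed switching, item shift, SD, correlation and number of pairs. The direction is probable rather than certain. Because the endpoint is secondary, the study is a pilot and the remedy is nearly free, the priority is CONSIDER.

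**What to change.** Keep the item wording. Add one stem to section A, in English and in any xi-Tsonga version, and use it identically at baseline and Month 7: *In these questions, doctors and health care workers means staff of clinics, hospitals and the government health service; do not include traditional healers.*

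A stem is preferable to rewriting the items as doctors and nurses at the clinic or hospital. That rewording would drop HIV counselors and community health workers and so narrow the allopathic construct. Leave section D unchanged: it asks about anticipated stigma, which this argument does not cover.

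If baseline collection has begun, do not change the wording midway. Add a Month 7 question on whom respondents had in mind when answering, and use it in a sensitivity analysis of the change in mistrust.

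The cost is one line on the tablet survey and its translation, and slightly less comparability with the published scale, from which the items are already adapted.
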